8.3.7. Timings of Assessment

Available data will be extracted from medical records from patients' visits per routine clinical care into the eCRF ([Table 1](#)). In addition, after the last study visit within routine care of each patient, physicians will provide a narrative/opinion on the benefit/risk profile of mepolizumab.

Table 1 Data Collection Plan for Core Variables

Variables	Pre-index period (12 months up to index date)	Index Date*	Routine Care Visits**
Informed Assent and Parent/Caregiver Consent	X		
Patient Eligibility	X		
Demographics	X		
EGPA/Treatment History	X		
Comorbidities/Concomitant Medications	X		X
Mepolizumab Treatment		X	X
Safety (AEs, SAEs, pregnancy exposures, medical device incidents)		X	X
Physician narrative/opinion on the benefit/risk profile of mepolizumab			X [#]
Additional variables to extract, if data is available: respiratory/cardiac involvement, absolute eosinophil counts, EGPA disease status, asthma exacerbations, PVAS, PVDI, spirometry results, hospital admissions	X	X	X

Abbreviations: AE=adverse event; EGPA=eosinophilic granulomatosis with polyangiitis; PVAS=Paediatric Vasculitis Activity Score; PVDI=Paediatric Vasculitis Damage Index; SAE=serious adverse event.

*Index date is defined as the date of the first dose of mepolizumab.

**Data will be extracted only if recorded as part of routine care visits.

[#]This will be drafted based on information extracted per this Table from routine care visits after the last study visit within routine care of each patient.

8.4. Data Sources

Clinical data of paediatric EGPA patients enrolled into this study from sites in selected countries across Europe will be extracted by Investigators or their designees. Given the ultra-rare nature of the condition and specialist knowledge needed for diagnosis and treatment, the most populous countries within Europe will be selected and sites within countries will be selected based on their EGPA expertise, i.e., specialised centres and

hospitals known to treat paediatric EGPA patients from the literature, and their catchment area. All data elements will be extracted from information routinely recorded in medical records into the eCRF by the Investigator or their designee for the purposes of the study. Where required, patient/guardian self-report, hospital discharge summaries or other relevant healthcare records will be requested by the investigator or site staff for all SAEs among enrolled patients. In addition, physicians will provide a narrative/opinion on the benefit/risk profile of mepolizumab.

8.5. Study Size

The sample size is not based on statistical power consideration but on an estimate based on a previous feasibility assessment performed by GSK and a literature review in PubMed. Based on existing patient registries, healthcare databases, published case-series [Mossberg, 2018; Iudici, 2015; Eleftheriou, 2016; Fina, 2018; Gendelman, 2013; GSK, data on file] and consultations with a paediatric rheumatologist expert, at most 13 paediatric EGPA patients may be identified across the participating sites from selected European countries in five years of whom about 10 patients might be prescribed mepolizumab and willing to participate. The feasibility of the study will be evaluated on an annual basis. Analyses for this study will be descriptive as the sample size will be insufficient to perform statistical tests.

8.6. Data Management

All information outlined in Section 8.3 will be extracted into the eCRF from medical records. In addition, physicians will provide a narrative/opinion on the benefit/risk profile of mepolizumab.

Data collection will be completed in a suitable electronic data capture (EDC) platform. All data extracted will be stored at secure servers ensuring compliance with local or national regulations. Database lock is anticipated on the date the study is closed, i.e., when all documents and data have been collected, and reviewed and necessary data changes have been made after the last study visit within routine care for the last patient. Additional details regarding data collection and validation procedures will be detailed in a data management plan.

The investigator is responsible for ensuring data is entered in a timely manner and verifying that data are accurate and correct. When the study is completed, the investigators must retain essential documents, e.g., source data that support information entered in the eCRF, for as long as needed to comply with regulatory guidelines and Sponsor requirements. The investigator must permit study-related monitoring, audits, institutional review board (IRB) review, and regulatory agency inspections and provide direct access to source data documents. The investigator will notify the Sponsor prior to moving or destroying any of the study documents. No records may be destroyed during the retention period without the written approval of the sponsor. No records may be transferred to another location or party without written notification to the sponsor.

8.7. Data Analysis

Data from this study will be described per patient as a case series, as the sample size will be insufficient to perform statistical analyses or summarise across patients.

8.7.1. Analysis Populations

8.7.1.1. Enrolled Population (EP)

The EP will consist of all patients for whom written informed assent as well as written informed consent from parents/caregivers has been obtained. The EP will be used to assess reasons for not initiating mepolizumab while being scheduled to initiate mepolizumab after enrolment.

8.7.1.2. Safety Population (SP)

The SP will include all patients in the EP who received at least one dose of mepolizumab. The SP will be the analysis population for descriptive, safety and effectiveness endpoints.

8.7.2. Statistical Methods

Given the ultra-rare nature of the disease, it is impractical to include a comparison group of EGPA patients who are not treated with mepolizumab in this study and so no formal hypotheses will be tested.

The primary analysis will present case reports of patients who initiated mepolizumab treatment at or after the enrolment start date. The primary analysis of prospective data will be supplemented with patients that had started mepolizumab prior to the enrolment start date (retrospective data) and will be presented separately.

8.7.2.1. Descriptive Analysis

Extracted data will be described per SP patient according to whether follow-up data was extracted before (retrospective) or after (prospective) enrolment. No further stratification will be conducted due to the small sample size. Missing data will not be imputed.

8.7.2.2. Analysis of Primary Objective

The primary objective for the study is to describe the real-world safety of mepolizumab treatment in paediatric EGPA patients during the follow-up period (see Section 8.3.1).

The following safety data will be described per SP patient according to whether follow-up data was extracted before (retrospective) or after (prospective) enrolment:

- AEs, SAEs and medical device incidents, and the corresponding number of events during the follow-up period; described by System Organ Class (SOC) and Preferred Term (PT) terms (MedDRA classification) as well as severity, seriousness, relationship to mepolizumab and outcome.
- All pregnancies during the follow-up period will be described.

8.7.2.3. Analysis of Secondary Objectives

The secondary objective for the study is to characterise paediatric EGPA patients treated with mepolizumab per routine clinical care in terms of demographics, clinical characteristics, medical and treatment history as well as real-world effectiveness of mepolizumab treatment in terms of the effect of mepolizumab on OCS dosage.

The following data will be described per SP patient **during the pre-index period**:

- Age (years) at diagnosis, mepolizumab initiation and enrolment
- Sex
- Ethnicity/Race
- Details of EGPA (symptoms and severity) at diagnosis, and at initiation of mepolizumab (EGPA status and duration of EGPA)
- EGPA management and concomitant medications (past 12 months)
- Absolute eosinophil count
- Comorbidities
- Additional variables to be described, if data is available:
 - EGPA American College of Rheumatology (ACR)/Lanham criteria at diagnosis
 - Number of asthma exacerbations (past 12 months)
 - PVAS and PVDI score at the index date
 - Baseline spirometry measurements (FEV1)
 - Number of hospital admissions (past 12 months) and length of stay

The following data will be described per SP patient according to whether follow-up data was extracted before (retrospective) or after (prospective) enrolment **during the post-index period**:

- Treatment data:
 - Mepolizumab treatment dose, duration of treatment (DoT), setting, formulation and (reasons for) discontinuation, dose delays/interruptions and dose changes
 - Daily OCS dose, DoT per formulation and (reasons for) discontinuation and dose changes
 - Immunosuppressant dose and DoT per type and formulation and (reasons for) discontinuation and dose changes
 - Other treatment type(s), dose(s), DoT and formulation(s)
- Physician narrative/opinion on the benefit/risk profile of mepolizumab including:
 - Comprehensive assessment of mepolizumab effectiveness as “effective”, “not effective” or “indeterminable” (including reasons) during the post-index treatment period (see definition Section 8.3.1).
- Additional outcomes to be described, if data is available:
 - Respiratory and cardiac involvement during follow-up
 - Absolute eosinophil counts (% change of baseline)
 - EGPA disease status (remission, relapse or refractory) during follow-up
 - Change from baseline in asthma exacerbations
 - Change from baseline in PVAS and PVDI
 - Change from baseline in spirometry measurement (FEV1).
 - Annual hospital admissions
 - Cumulative hospital admission length of stay

8.8. Quality Control and Quality Assurance

To ensure compliance with all applicable regulatory requirements, the Sponsor may conduct a quality assurance audit. See Section 8.8.5 for more details regarding the audit process.

8.8.1. Data Quality Assurance

Syneos Health and GSK are responsible for following standard operating procedures (SOPs) to ensure data quality and integrity, including archiving of statistical programs, appropriate documentation of data cleaning and validity for created variables, and description of available data. All sites will be trained by the Site Management Associate (SMA) on the protocol, study logistics, and the EDC system. Investigators will be reminded of the processes and importance of reporting all safety events (AEs, SAEs, pregnancy exposures and medical device incidents) and other information.

Data collection during this study will be managed using a software tool designed to ensure quality assurance and facilitate data capture during clinical studies. The investigator is responsible for ensuring prospective data is entered in a timely manner and verifying that data are accurate and correct by physically or electronically signing the eCRF.

On-line logic checks will be built into the EDC system as much as possible, so that missing or illogical data are not submitted. In the event that inconsistent data persist, queries may be issued electronically to the clinical study centre and answered electronically by that study centre's personnel.

This study will be conducted according to GSK SOP52213 (Conducting Quality Control Review of Study Results generated using Existing Data in Value, Evidence and Outcomes [VEO] and US VEO). This procedure requires documented evidence that the study protocol has been correctly interpreted and executed.

An independent QC analyst will document their review of the work of the Project Analyst. Analysts will reach and document agreement that the study results are complete, internally consistent, and accurately reflect the source data and intended purpose of this protocol.

8.8.2. Access to Source Data/Documents

The Investigator will allow Sponsor representatives, contract designees, authorised regulatory authority inspectors, and IRB to have direct access to all documents pertaining to the study.

8.8.3. Archiving Study Documents

Essential clinical documents will be maintained to demonstrate the validity of the study and the integrity of the data extracted. All study materials will be returned to the Sponsor after the study has been completed.

Master files should be established at the beginning of the study, maintained for the duration of the study, and retained according to the appropriate regulations. According to International Council on Harmonisation (ICH) guidelines, essential documents should be retained for a minimum of 2 years after the last approval of a marketing application in an ICH region and until there are no pending or contemplated marketing applications in an ICH region or at least 2 years have elapsed since the formal discontinuation of clinical development of the study treatment.

8.8.4. Study Monitoring

Participating sites will be queried every 12 months from study start to check for newly diagnosed paediatric EGPA patients who initiated treatment with mepolizumab in the previous 12 months.

Patient data will be monitored remotely. Monitoring visits may be scheduled throughout the study, if needed. Monitoring visits will be scheduled in advance, to ensure that the investigator has sufficient time to meet with the SMA and discuss all relevant findings. Patient data will be reviewed and/or audited, and all deficiencies corrected on site, if possible. A complete audit trail of all monitoring visits and data changes will be maintained. A virtual close-out visit will be scheduled when all documents and data have been collected, reviewed and necessary data changes have been made after the last study visit within routine care for the last patient. If the study is terminated, a virtual study close-out visit may be scheduled with the site if needed to retrieve all remaining study records. As long as COVID-19 restrictions apply, on-site study initiation and monitoring visits will not be scheduled until restrictions are alleviated.

The SMA will review the study conduct to determine compliance with the study protocol. The SMA will review and/or audit the electronic forms and source documents to ensure the accuracy and completeness of the data captured for the study. The SMA will review the informed patient assent and parent/caregiver consent forms (ICFs) to ensure that no forms were signed prior to the date of IRB approval of the study. The system for record-keeping will be reviewed.

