3.8. Study Size

Based on existing patient registries, healthcare databases and published case-series, at most 13 paediatric EGPA patients are expected to be diagnosed over a five-year period across the selected European countries of whom about 10 patients might be prescribed mepolizumab and willing to participate. The feasibility of the study will be evaluated on an annual basis.

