8. RESEARCH METHODS

8.1. Study Design

This multinational, multi-site, case-series will aim to collect data on real-world safety and effectiveness up to 24 months after the initiation of mepolizumab treatment in paediatric EGPA patients in Europe. In addition, demographic and relevant medical history data will be collected up to 12 months prior to the first dose of mepolizumab.

EGPA in a paediatric population is extremely rare, and there will be challenges in identifying and recruiting eligible patients. The study design reflects these challenges. All eligible paediatric EGPA patients aged 6-17 years who initiated mepolizumab in the 12 months prior to the enrolment start date (regardless of whether they continue treatment following study enrolment or not), or who will initiate mepolizumab treatment at or after the enrolment start date will be invited for study enrolment by their treating physicians. These physicians will be from specialised centres and hospitals known to treat paediatric EGPA patients from selected countries in Europe. As the study is non-interventional, the decision to treat paediatric EGPA patients with mepolizumab will be made prior to and

independent from the decision to enrol patients into the study, and baseline and follow-up assessments will be in accordance with local standard medical care.

Per the local regulatory requirements, informed consent for minors (defined by the country law) will be obtained from the parent/caregiver with confirmation (assent) from the minor that he/she wishes to participate before enrolment into the study.

After obtaining informed consent from parents/caregivers and assent from paediatric patients, they will be enrolled into the study and data will be extracted from medical records and entered in an eCRF, where applicable.

Depending on the time point of the initiation of mepolizumab treatment in relation to the enrolment start date (i.e., the study start date), data for the primary and secondary objectives will be collected either prospectively (primary analysis) and/or retrospectively (supplemental analysis).

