8.2.1. Inclusion Criteria

A patient who meets **all** of the following criteria is eligible for inclusion:

- Written informed assent and parent/caregiver consent
- Male or female, aged 6 to 17 years at the start of mepolizumab treatment
- Confirmed diagnosis of EGPA
- Initiated mepolizumab up to 12 months prior to enrolment start date (regardless of whether they continue treatment following study enrolment or not) or scheduled to receive treatment with mepolizumab at or after enrolment per routine clinical care

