8.2.2. Exclusion criteria

A patient who meets **any** of the following criteria is not eligible for inclusion:

- Concurrent enrolment and/or participation in an interventional clinical trial involving either an investigational medicinal product or medical device
- Received treatment with mepolizumab more than 12 months prior to enrolment start date
- Received other biologics within 3 months of the first dose of mepolizumab.

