8.3.2. Baseline Characteristics

Baseline characteristic data at the date of the first mepolizumab dose (i.e., the index date) or up to 12 months prior to the first mepolizumab dose (i.e., the pre-index period) will be extracted if available from routine care visits at study enrolment.

The following data will be recorded where available:

- Demographics:
 - Age (at diagnosis, at mepolizumab initiation and at enrolment)
 - Sex
 - Race/ethnicity
 - Height/weight at mepolizumab initiation
- Clinical characteristics at diagnosis (most recent data available up to 12 months before or at diagnosis):
 - EGPA disease characteristics
 - Asthma with eosinophilia
 - Neuropathy
 - Pulmonary infiltrates
 - Sinonasal abnormality
 - Cardiomyopathy
 - Palpable purpura
 - ANCA-positive status
- Clinical characteristics at the index date (most recent data available up to 12 months before or at initiation of mepolizumab):
 - Absolute eosinophil count
 - EGPA disease status (remission, relapsing, refractory) according to European League Against Rheumatism (EULAR) criteria [[Hellmich, 2007](#)], if feasible, or to local standard practice
 - EGPA disease features based on the Chapel Hill Consensus Conference (CHCC) 2012 nomenclature system [[Jennette, 2013](#)]
 - Comorbidities at the index date (most recent data available up to 12 months before or at the index date)
- Treatment history regarding EGPA disease management (specifically OCS and immunosuppressants) and concomitant medications 12 months prior to the index date: type(s), start date(s), dose(s) and formulation(s)
- Additional variables to extract, if data is available:
 - EGPA American College of Rheumatology (ACR)/Lanham criteria at diagnosis
 - Asthma exacerbations prior to the index date defined as exacerbations of bronchial asthma which require hospitalisation, an emergency room visit or use of systemic steroids (any increase in dose that are higher than the maintenance OCS dose)
 - PVAS and PVDI score at the index date
 - Spirometry measurement results (FEV1) at the index date (most recent data available up to 12 months before or at the index date)
 - Hospital admissions at the index date (number, length of stay, primary reason for hospitalisation, ward type[s])

The World Health Organization (WHO) Drug Dictionary for medications will be used for coding drugs. The Medical Dictionary for Regulatory Activities (MedDRA) will be used for coding concomitant diseases.

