8.9. Limitations of the Research Methods

8.9.1. Selection Bias

All eligible paediatric EGPA patients treated with mepolizumab from sites in Europe will be invited for study enrolment including patients who discontinued mepolizumab treatment before enrolment to reduce selection bias. Reasons for patient non-

participation, withdrawal or loss-to-follow-up will be recorded in the eCRF, if available, to address any remaining selection bias.

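### The 12-monthly site query in Section 8.8.4 asks only about newly diagnosed children, although eligibility sets no limit on time since diagnosis, so it cannot verify that longer-standing patients who start mepolizumab were all invited

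*Protocol*

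**What the plan says.** Protocol Section 8.8.4 (Study Monitoring) has participating sites queried every 12 months from study start "to check for newly diagnosed paediatric EGPA patients who initiated treatment with mepolizumab in the previous 12 months". Both conditions, a recent diagnosis and a recent start of mepolizumab, define the child the site is asked about.

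Eligibility is wider. Section 8.2.1 asks for "Confirmed diagnosis of EGPA", with no limit on how long ago the diagnosis was made. Its time criterion concerns treatment: "Initiated mepolizumab up to 12 months prior to enrolment start date", or treatment scheduled at or after enrolment. The time limits in Section 8.2.2 concern earlier mepolizumab ("Received treatment with mepolizumab more than 12 months prior to enrolment start date") and other biologics, not disease duration.

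Section 8.1 gives the recruitment route: eligible patients "will be invited for study enrolment by their treating physicians". Section 8.9.1 relies on that route for completeness: "All eligible paediatric EGPA patients treated with mepolizumab from sites in Europe will be invited for study enrolment", including those who stopped mepolizumab before enrolment, as the means of reducing selection bias.

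**The concern.** The query and the eligibility criteria describe different groups. A child diagnosed three years ago who starts mepolizumab this year is eligible but does not fit the query.

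The protocol expects such children. Section 8.3.2 records "EGPA disease status (remission, relapsing, refractory") at the index date, and Section 8.7.2.3 describes the duration of EGPA at initiation for each patient.

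What is at stake is whether the series can be shown to be complete. In a case series with no comparator, the claim that every eligible patient was approached is the main protection against selection. A check that leaves out one disease stage cannot support that claim for that stage. Children with longer disease may also have had more steroid and immunosuppressant treatment before mepolizumab, which is relevant to the secondary objective on OCS dosage.

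**Working it through.** **The plan's own figure.** Sections 3.8 and 8.5 expect about 10 participants out of at most 13 patients. This is a feasibility judgement without a formula. The implied share is 10/13 = 76.9%, which the protocol does not state. Nothing in this point changes it.

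**Step 1: compare scopes.**

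| Condition | Eligibility (8.2.1, 8.2.2) | Site query (8.8.4) |
|---|---|---|
| Diagnosis | Confirmed, any duration | Recent only |
| Mepolizumab start | From 12 months before the enrolment start date onwards | Previous 12 months |
| Stopped treatment since | Still eligible | Not mentioned |

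The diagnosis row is the mismatch. Eligible patients whose diagnosis is not recent fall outside the query.

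**Step 2: look for another check that covers them.**

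- Reasons for non-participation (8.9.1, 9.1) are recorded for patients who decline, so they arise only after an invitation.
- The site management associate's review (8.8.4) covers protocol compliance, captured data and consent forms. No review of treated but unenrolled patients is described.
- The annual reviews (8.9.5) look at study progress and patient numbers. They do not ask sites who was not invited.

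None of these would reveal a long-standing patient who started mepolizumab and was never invited.

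**Step 3: illustrate the size.** The protocol gives neither quantity needed, so both are assumptions:

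- N = 10 eligible starters, taken from the expected enrolment;
- q = share of starters who are not newly diagnosed, assumed 20% to 60%;
- c = share of those whom their physician invites anyway, assumed 50% to 100%.

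Formulas: outside the query = N × q; expected number missed = N × q × (1 − c); P(at least one missed) = 1 − [1 − q(1 − c)]^N.

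Example: q = 40%, c = 80% gives 10 × 0.4 × 0.2 = 0.8 expected missed, and P = 1 − 0.92^10 = 0.566.

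Expected number missed, with P(at least one missed) in brackets:

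| q | Outside query | c = 50% | c = 80% | c = 95% | c = 100% |
|---|---|---|---|---|---|
| 20% | 2 | 1.0 (0.651) | 0.4 (0.335) | 0.1 (0.096) | 0 (0) |
| 40% | 4 | 2.0 (0.893) | 0.8 (0.566) | 0.2 (0.183) | 0 (0) |
| 60% | 6 | 3.0 (0.972) | 1.2 (0.721) | 0.3 (0.263) | 0 (0) |

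Between 2 and 6 of 10 patients could lie outside the query, but the number actually lost runs from 0 to 3. At any given q, it depends wholly on how complete physician invitation is, which is what the query could have helped to verify. Each patient lost is 1/10 = 10% of the series.

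**The case against.** The strongest reply is that enrolment does not run through the query. Physicians at specialised centres invite every eligible patient whatever the disease duration, all sites are trained on the protocol (8.8.1), and the query is a monitoring step added to that route. This stands. A reader might infer from Section 8.8.4 that longer-standing patients are missed, or that the 8.9.1 statement is false. The protocol supports neither; it shows only that the check is blind to these children. Specialist sites may also know their long-standing patients well, so nothing shows that they are more likely to be overlooked than new cases. Data are described per patient (8.7), so there is no pooled estimate to bias, and Section 8.9.2 already limits the conclusions.

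Three further inferences are tempting but not supported:

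- **A gap in the first year.** If the first query comes at month 12, its look-back would not reach children who started before study start. The timing wording can equally mean a first query at study start, which would cover them. It needs clarifying but is not a demonstrated gap.
- **A planning figure that is too low.** Section 3.8 says "at most 13 paediatric EGPA patients are expected to be diagnosed over a five-year period". One could compute 13/5 = 2.6 per year and 2.6 × 6 = 15.6 over six years of starts. But Section 8.5 speaks of patients identified, not diagnosed; the calculation treats diagnoses as mepolizumab starts; and study size is not power-based, so nothing downstream changes.
- **Relapse rate as a measure of q.** The 64.3% in Section 6.1.1 is background on relapse and does not say when mepolizumab is started.

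The objection does not remove the mismatch itself. If the wording was loosely meant as newly identified, sites may still apply it as written.

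**Conclusion.** The point holds as a mismatch between Section 8.8.4 and Sections 8.2.1 and 8.2.2. The only periodic check for eligible patients leaves out those whose diagnosis is not recent, a group the protocol admits and plans to describe. An uninvited child in that group would go undetected, any such loss would be selective by disease stage, and completeness as stated in Section 8.9.1 cannot be verified for them.

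The number affected cannot be derived from the protocol, and the 0 to 3 range rests on assumed values of q and c. It is zero if physicians invite everyone as planned. What is firm is that each loss would matter in a series of about 10, and that Section 5 allows early closure for low recruitment. The correction is worth making because it is nearly free, not because a loss has been shown.

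**What to change.** In Section 8.8.4, replace the restriction to recent diagnoses so that sites are asked for all paediatric EGPA patients, regardless of date of diagnosis, who initiated mepolizumab in the previous 12 months, including those who have since stopped. State that the first query covers the 12 months before the enrolment start date, so that it matches the window in Section 8.2.1.

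No eligibility criterion, study procedure or planned number changes. The cost is one reworded sentence and slightly longer record searches at a few specialist sites.
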